- b) State what the Investigator(s) hope to learn from the study. Include an assessment of the importance of this new knowledge.**

We will learn how different lengths of night float affects a resident's activity level, sleep and self reported wellness. These objective measurements can be used to assess targets for intervention with an altered call paradigm or increased support to prevent long term disability from changes identified. In the long term, we hope to reduce physician burnout and improve physician wellness.

- c) Explain why human subjects must be used for this project. (i.e. purpose of study is to test efficacy of investigational device in individuals with specific condition; purpose of study is to examine specific behavioral traits in humans in classroom or other environment)**

The purpose of the study is the examine specific behavioral patterns, specifically sleep pattern and activity level, in humans who are working during a night shift system.

2. Study Procedures

- a) Please SUMMARIZE the research procedures, screening through closeout, which the human subject will undergo. Refer to sections in the protocol attached in section 16, BUT do not copy the clinical protocol. Be clear on what is to be done for research and what is part of standard of care.**

Participants will be recruited via an email once they are scheduled for a week of night float in the Stanford Main Operating room or Obstetric anesthesia. Potential participants who are taking prescription medications that might affect their alertness during the study period will not be enrolled.

We will quantify the changes in sleep pattern and activity during the week before, during, and after the night float call week. Self reported aspects of well being including fatigue, physical function, and positive affect will be assessed with NIH PROMIS surveys at the end of each week during the study period.

We will use the Fitbit Alta HR to quantify the change in total amount of sleep, sleep interruption and sleep phase and steps per day. Data will be analyzed only when it is coincident with heart rate data to correct for periods when the device is not used.

Activity will not alter from the participants normal except that they will wear the Fitbit and respond to the NIH PROMIS surveys over the study period. After completing all surveys and returning the fitbit, the participants will receive a \$10 gift certificate as a recognition for their time.

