Based on their rotation schedule, they will have the option to wear the Fitbit for an additional 3 weeks for additional data collection.

Data from NIH PROMIS surveys, Fitbit and provided demographic

Title : Effect of Night Float Call on Sleep and Activity Patterns Among Anesthesia Residents
Approval Period: 08/19/2020 - 12/31/2999

information including age, sex and BMI, and number of previous night float periods previously completed. After association, data will be completely deidentified.

All data will be normalized to the participant's baseline values during the run-in week. The call week and post call week will be analyzed with a time series mixed effects model using R and/or NONMEM (a program for Nonlinear Mixed Effects Modeling). The effects of the above demographic variables will be assessed as potential covariates.

The intended goal of this project is to improve the current resident call structure within the anesthesia department (QI); however, we are applying for IRB approval because we believe that the data gathered about the impact of night float on sleep patterns and physician well-being can be generalized and we would want to publish this data in the future. We anticipate that this observational study will be the first of many studies looking at the effects of changing sleep patterns on activity and well-being

b) Explain how the above research procedures are the least risky that can be performed consistent with sound research design.

Our research protocol constitutes very low risk to participants because it does not require that they deviate from their usual behavior pattern. There is always a remote risk that data confidentiality will be breached. Steps taken to prevent that risk are data storage in Redcap and only using de identified data for analysis. All investigators have or will ([name]) complete CITI training prior to study initiation.

c) State if deception will be used. If so, provide the rationale and describe debriefing procedures. Since you will not be fully informing the participant in your consent process and form, complete an alteration of consent (in section 13). Submit a debriefing script (in section 16).

N/A

d) State if audio or video recording will occur. Describe what will become of the recording after use, e.g., shown at scientific meetings, erased. Describe the final disposition of the recordings.

N/A

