If medical equipment used for human patients/participants is also used on animals, describe such equipment and disinfection procedures.

We will use the commercially available Fitbit Alta HR activity tracker according to its intended use to track physical activity and sleep. Between each individual user, the Fitbit will be rinsed with water and wiped with a small amount of rubbing alcohol as per the Fitbit Wear & Care guidelines (<https://www.fitbit.com/product-care#:~:text=FOR%20ELASTOMER%20BANDS%3A&text=Do%20NOT%20use%20hand%20soap>) In light of the current COVID-19 pandemic, we will also allow at least 72 hours between each user. The devices will not be used on animals.

8. Participant Population

- a) State the following: (i) the number of participants expected to be enrolled at Stanford-affiliated site(s); (ii) the total number of participants expected to enroll at all sites; (iii) the type of participants (i.e. students, patients with certain cancer, patients with certain cardiac condition) and the reasons for using such participants.

We aim to recruit 40-60 participants. The sample size is a convenience sample based on interest by half of all residents eligible. All participants enrolled will be anesthesia residents currently rotating in the Stanford Main Operating Rooms or on OB anesthesia

- b) State the age range, gender, and ethnic background of the participant population being recruited.

We will recruit participants who are PGY2-5, which means they will generally be between 26-36 years of age. We will aim to recruit an equal number of males and females which is reasonable given the demographic distribution of Anesthesia residents. Finally, we aim to have a people with a variety of races and ethnicity involved but this will not be specifically targeted or evaluated due to the limited pool of eligible subjects.

- c) State the number and rationale for involvement of potentially vulnerable subjects in the study (including children, pregnant women, economically and educationally disadvantaged, decisionally impaired, homeless people, employees and students). Specify the measures being taken to minimize the risks and the chance of harm to the potentially vulnerable subjects and the additional safeguards that

Title : Effect of Night Float Call on Sleep and Activity Patterns Among Anesthesia Residents
Approval Period: 08/19/2020 - 12/31/2999

have been included in the protocol to protect their rights and welfare.

n/a

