- j) Describe how you will be cognizant of other protocols in which participants might be enrolled. Please explain if participants will be enrolled in more than one study.**

We will not enroll participants who are currently enrolled in other studies.

- k) Payment/reimbursement. Explain the amount and schedule of payment or reimbursement, if any, that will be paid for participation in the study. Substantiate that proposed payments are reasonable and commensurate with the expected contributions of participants and that they do not constitute undue pressure on participants to volunteer for the research study. Include provisions for prorating payment. See payment considerations**

Participants who complete the study will be compensated with \$10 gift card at completion of final survey. We consider this to be an appreciation gift at a token level.

- l) Costs. Please explain any costs that will be charged to the participant.**

The participant will not be expected to incur any costs while participating in the study. The Fitbits will be

Title : Effect of Night Float Call on Sleep and Activity Patterns Among Anesthesia Residents
Approval Period: 08/19/2020 - 12/31/2999

provided by [name] that have been used in a previous study.

- m) Estimate the probable duration of the entire study. Also estimate the total time per participant for: (i) screening of participant; (ii) active participation in study; (iii) analysis of participant data.**

We anticipate that this study will take two years. Screening of each participant will take approximately 30 minutes, we will track their sleep and activity for 3-6 weeks, and 3 surveys will take no more than 5 minutes each and will be delivered with a web link sent by Redcap. We anticipate we will spend 20 hours analyzing all of the collective data per participant.

9. Risks

- a) For the following categories include a scientific estimate of the frequency, severity, and reversibility of potential risks. Wherever possible, include statistical incidence of complications and the mortality rate of proposed procedures. Where there has been insufficient time to accumulate significant data on risk, a statement to this effect should be included. (In describing these risks in the consent form to the participant it is helpful to use comparisons which are meaningful to persons unfamiliar with medical terminology.)

The risks of the Investigational devices.

N/A. This is not an investigational device.

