- d) Explain the point at which the experiment will terminate. If appropriate, include the standards for the termination of the participation of the individual participant Also discuss plans for ensuring necessary medical or professional intervention in the event of adverse effects to the participants.**

Because this project is observational only, we do not anticipate the need for termination of the participation of the individual participant. However, if any unforeseen complications occur, such as personal illness or emergency, that they were not able to complete the study period, we would exclude them from the analysis. The participant can take the device off at any time.

10. Benefits

- a) Describe the potential benefit(s) to be gained by the participants or by the acquisition of important knowledge which may benefit future participants, etc.**

Potential benefits of the study include:

- Contribution to our understanding of the impact of call paradigms on trainee wellness
- Fitness trackers have been shown to increase a user's activity levels
- Increased insight into your sleep patterns and daily activity levels
- Opportunity to learn about healthy sleep habits

11. Privacy and Confidentiality

Privacy Protections

- a) Describe how the conditions under which interactions will occur are adequate to protect the privacy interests of participants (e.g., privacy of physical setting for interviews or data collection, protections for follow-up interactions such as telephone, email and mail communications).**

All demographic information and PROMIS surveys will be administered, collected and stored in Redcap as this method is approved by Stanford for data security. The data will be coded and only be accessed via secure Stanford University-approved computer that is up to date with the necessary school of medicine privacy software. We will communicate via secure messaging if any PHI is involved.

Confidentiality Protections

- b) Specify PHI (Protected Health Information). PHI is health information linked to HIPAA identifiers**

Title : Effect of Night Float Call on Sleep and Activity Patterns Among Anesthesia Residents
Approval Period: 08/19/2020 - 12/31/2999

(see above). List BOTH health information AND HIPAA identifiers. If you are using STARR, use the Data Privacy Attestation to ensure that your request will match your IRB-approved protocol. Be consistent with information entered in section 15a.

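### A resident who cannot complete the study period is dropped whole, although the planned mixed model could use that resident's valid night float days

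*Protocol*

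**What the plan says.** Protocol section 9 d) sets the rule. Its trigger is narrow, "if any unforeseen complications occur, such as personal illness or emergency", and its consequence is stated for the participant and not for the affected days: "that they were not able to complete the study period, we would exclude them from the analysis". No other section keeps the data already collected from such a resident.

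Section 2 a) describes the data and the analysis:

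- Baseline: "All data will be normalized to the participant's baseline values during the run-in week".
- Model: "The call week and post call week will be analyzed with a time series mixed effects model".
- Device non-wear: "Data will be analyzed only when it is coincident with heart rate data".
- Surveys: well-being "will be assessed with NIH PROMIS surveys at the end of each week during the study period".

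Section 8 a) gives the size: "We aim to recruit 40-60 participants. The sample size is a convenience sample". Item 1 of the Modification form reports 12 residents enrolled and 40 more sought, and gives adequate power as the reason.

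**The concern.** The exclusion rule and the planned analysis do not fit together. The analysis needs a run-in baseline and some call-week observations from each resident; it does not need a complete series. Take a resident with seven run-in days and seven night float days who falls ill in the post-call week. That resident has supplied everything needed to estimate the call-week change, yet contributes nothing under section 9 d). A resident who merely left the device off on the same post-call days stays in, because the heart rate rule removes records and not people.

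Two things are at stake. The first is precision, which is lost whenever an excluded resident has a baseline and at least one valid call day. The second is a possible bias. If residents who react worst to night float are also less likely to finish, the completers-only estimate understates the effect. The protocol neither shows nor excludes such a link.

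**Working it through.** **Inputs from the protocol.** One week each of run-in, night float and post-call (Resources, d), so 7 + 7 + 7 = 21 days. Target 40 to 60 (section 8 a). Enrolled plus sought: 12 + 40 = 52, which lies within the target. The sample size is one of convenience, so there is no power calculation to reproduce.

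**Assumed inputs.** The protocol gives no non-completion rate and no variability. I take daily sleep as the example, with a between-resident SD of the call-week effect of 0.8 h, a day-to-day SD of 1.4 h, and 3, 5 or 8 exclusions.

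**1. Precision.** For the change from the resident's own seven-day run-in mean, with n valid call days:

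variance per resident = 0.8² + 1.4²/7 + 1.4²/n

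- n = 7: 0.64 + 0.28 + 0.28 = 1.20
- n = 3: 0.64 + 0.28 + 0.653 = 1.573
- n = 1: 0.64 + 0.28 + 1.96 = 2.88

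Relative to a complete resident, inverse-variance weights are 1, 1.20/1.573 = 0.763 and 1.20/2.88 = 0.417. With N residents, k of them excluded and w the weight each would have had, the standard error rises by the factor √[(N − k + k·w)/(N − k)].

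For N = 52 and k = 8:

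- Full call week: √(52/44) = 1.087. The standard error goes from √(1.20/52) = 0.1519 h to √(1.20/44) = 0.1651 h.
- One call day: √[(44 + 8 × 0.417)/44] = 1.037.

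| Excluded from 52 | 7 call days | 3 call days | 1 call day |
|---|---|---|---|
| 3 | 3.0% | 2.3% | 1.3% |
| 5 | 5.2% | 4.0% | 2.2% |
| 8 | 8.7% | 6.7% | 3.7% |

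Over the 40 to 60 target, the range runs from 1.1% (3 of 60, one call day) to 11.8% (8 of 40, full call week). Varying the effect SD over 0.5 to 1.2 h or the daily SD over 1.0 to 1.8 h moves the 8-of-52 figures to 6.0–7.4% (three call days) and 2.9–4.8% (one call day). A resident who leaves during run-in costs nothing under the run-in normalisation.

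**2. Averaging over when residents leave.** If the last observed day is spread evenly over days 0 to 20, 13 of 21 non-completers (62%) have a full baseline and at least one call day. Days 8 to 13 give n = 1 to 6, with weights 0.417, 0.632, 0.763, 0.851, 0.915 and 0.963. Days 14 to 20 give weight 1 each. The mean weight is (4.54 + 7)/21 = 0.549. With a proportion d not completing, the factor is √[1 + 0.549·d/(1 − d)], an increase of 1.4, 3.0 or 6.6% at d = 5, 10 or 20%.

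**3. Conditional bias.** Let non-completion follow a logistic model in the resident's own loss of sleep. The table shows by how much the completers-only effect is too small, in minutes per day (numerical integration).

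| Effect SD | Odds of non-completion per extra hour lost | 5% | 10% | 20% |
|---|---|---|---|---|
| 0.8 h | ×1 (no link) | 0 | 0 | 0 |
| 0.8 h | ×1.64 | 0.9 | 1.9 | 3.7 |
| 0.8 h | ×2.7 | 1.8 | 3.6 | 6.9 |

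One standard error here is about 9 to 10 min (0.1519 h × 60 = 9.1; 0.1651 h × 60 = 9.9). At 10% and odds ×2.7, an effect SD of 0.5 to 1.2 h gives 1.5 to 7.5 min. The most extreme combination tried (SD 1.2 h, ×2.7, 20%) gives 14.1 min, against a standard error of about 12 to 13 min.

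**4. The alternative rule.** It was simulated with 52 residents, a true effect of −1.0 h, 20,000 runs per setting, and last valid days spread over the call and post-call weeks. At odds ×2.7 and 5, 10 and 20% non-completion, completers-only gave −0.969, −0.940 and −0.885 h; retaining valid days gave −0.997, −0.995 and −0.990 h. With no link both gave −1.00 h, and the completers-only estimate was more variable by 2.3, 5.1 and 11.0%.

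**The case against.** The strongest reply is that the harm is small and the trigger rare. Section 9 d) covers only unforeseen complications and itself expects no need to end anyone's participation. The participants are healthy residents wearing a tracker, and ordinary non-wear does not trigger exclusion. The 11.8% figure needs 8 of 40 residents to stop, each after a full call week, and nothing in the protocol supports that rate; the averaged 1.4 to 6.6% is fairer. The bias depends entirely on assumed inputs. All of this stands, and it limits the size of the point. It does not give a reason for the rule, because omitting the affected days would meet the same purpose.

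Three narrower objections also have some force:

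- Surveys come at the end of each week, so a resident who leaves mid-call-week has no call-week survey, and retention adds nothing there.
- Omitting illness days is itself selection on an event after exposure, if night float contributes to illness. A sensitivity analysis that keeps those days addresses this in part.
- The simulation in step 4 gives every non-completer some call data, which favours the alternative. The precision figures likewise assume a seven-day baseline.

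**Conclusion.** The concern holds. The protocol fixes an analysis set that discards valid exposure data which its own model can use. The loss of precision follows from the rule whenever an excluded resident has a baseline and a valid call day. Under the assumed variances it is about 1 to 12% of the standard error, and 1.4 to 6.6% at 5 to 20% non-completion with evenly spread timing. Bias is a possibility and not a demonstrated fault: zero without a link between response and non-completion, and below one standard error in all but the most extreme scenario tried. Confidence is high that the rule exists and is unnecessary. Its size cannot be settled from the protocol. It should be fixed because the sample is small, the sponsor is enrolling more residents for power, and the repair is cheap.

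**What to change.** Replace the exclusion clause in section 9 d) with wording to this effect:

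> All heart-rate-valid Fitbit days and surveys from participants with a run-in baseline who worked at least one night float shift stay in the mixed model up to the point of non-completion. Days of reported illness or leave are recorded and omitted from the main analysis. The number, timing and reasons of non-completion are reported. A completers-only analysis and an analysis keeping the illness or leave days are sensitivity analyses.

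State the minimum number of valid run-in days that counts as a baseline. Add one line saying that, for this rule, the study period is the run-in, call and post-call weeks. Section 8 m) allows 3 to 6 weeks of tracking, but its survey count ("3 surveys will take no more than 5 minutes each") together with weekly surveys already implies three weeks.

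The cost is a few sentences and an IRB modification, which the Obligations section requires for any change. Dates of illness or leave and reasons for non-completion must be collected. As health information, they may also need adding to the list in section 11 b). The new estimate relies on data being missing at random. If non-completion depends on the individual response itself, a small bias remains: 0.2, 0.3 or 0.6 min at 5, 10 or 20% in the odds ×2.7 simulation.

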13.1 Consent Sleep Study Consent Form 08/2020

Sponsor's Consent Version Number: (if any) : 3

- a) Describe the informed consent process. Include the following.
 - i) Who is obtaining consent? (The person obtaining consent must be knowledgeable about the study.)

Title : Effect of Night Float Call on Sleep and Activity Patterns Among Anesthesia Residents
Approval Period: 08/19/2020 - 12/31/2999

- ii) When and where will consent be obtained?
- iii) How much time will be devoted to consent discussion?
- iv) Will these periods provide sufficient opportunity for the participant to consider whether or not to participate and sign the written consent?
- v) What steps are you taking to minimize the possibility of coercion and undue influence?
- vi) If consent relates to children and if you have a reason for only one parent signing, provide that rationale for IRB consideration.

i) Either [name] or [name] ii) consent will be obtained in person at the beginning of the study iii) at least 10 minutes, longer if participant has additional questions. The consent form will also be provided for the participant to read ahead of time iv) yes V) participation is completely voluntary. they are only receiving a nominal participation gift card, and initial recruitment is via email so we hope there is no pressure to respond to them email if unwilling to participate vi) no children will participate in this study

- b) **What is the Procedure to assess understanding of the information contained in the consent? How will the information be provided to participants if they do not understand English or if they have a hearing impairment? See HRPP Chapter12.2 for guidance.**

We do not anticipate any non-english speakers to participate in this study. All participants will be residents with medical degrees

- c) **What steps are you taking to determine that potential participants are competent to participate in the decision-making process? If your study may enroll adults who are unable to consent, describe (i) how you will assess the capacity to consent, (ii) what provisions will be taken if the participant regains the capacity to consent,(iii) who will be used as a legally authorized representative, and (iv) what provisions will be made for the assent of the participant.**

We do not anticipate enrolling any participants who are unable to consent for themselves

14. Assent Background (less than 18 years of age)

15. HIPAA Background

16. Attachments

Attachment Name	Attached Date	Attached By	Submitted Date
PROMIS Fatigue	07/07/2019	[name]	
PROMIS Positive Affect	07/07/2019	[name]	
PROMIS Sleep Disturbance	07/07/2019	[name]	
51495 [name] Academic Sponsor Review	07/08/2019	[name]	
Participant Demographic Survey	07/19/2019	[name]	
Recruitment email v 3.0	08/08/2020	[name]	

Obligations

Title : Effect of Night Float Call on Sleep and Activity Patterns Among Anesthesia Residents
Approval Period: 08/19/2020 - 12/31/2999

The Protocol Director agrees to:

- Adhere to principles of sound scientific research designed to yield valid results
- Conduct the study according to the protocol approved by the IRB
- Be appropriately qualified to conduct the research and be trained in Human Research protection, ethical principles, regulations, policies and procedures
- Ensure all Stanford research personnel are adequately trained and supervised
- Ensure that the rights and welfare of participants are protected including privacy and confidentiality of data
- Ensure that, when de-identified materials are obtained for research purposes, no attempt will be made to re-identify them.
- Disclose to the appropriate entities any potential conflict of interest
- Report promptly any new information, modification, or unanticipated problems that raise risks to participants or others
- Apply relevant professional standards.

Any change in the research protocol must be submitted to the IRB for review prior to the implementation of such change. Any complications in participants or evidence of increase in the original estimate of risk should be reported at once to the IRB before continuing with the project. Inasmuch as the Institutional Review Board (IRB) includes faculty, staff, legal counsel, public members, and students, protocols should be written in language that can be understood by all Panel members. The investigators must inform the participants of any significant new knowledge obtained during the course of the research.

IRB approval of any project is for a maximum period of one year. For continuing projects and activities, it is the responsibility of the investigator(s) to resubmit the project to the IRB for review and re-approval prior to the end of the approval period. A Notice to Renew Protocol is sent to the Protocol Director 7 weeks prior to the expiration date of the protocol.

